1.5 Dose Rationale and Risk/Benefits

RhDNase1 1mg/ml (0.1%) will be applied topically to the ocular surface as eye drops. This is the same dose as is currently in use in patients with Cystic Fibrosis. The drug formulation is being used unchanged. This dose has been effective in reducing eDNA content when given to patients with cystic fibrosis. We do not expect any serious adverse events with this dose.

Drugs are routinely applied topically to the ocular surface as eye drops because of easy access to the ocular tissues and good drug bioavailability. Therefore, we will use rhDNase1 topically. We have chosen an eight week duration of therapy because we expect rhDNase1 to be used continually; eight weeks of treatment will give us better data to predict side effects during long-term use. Since rhDNase1 is not expected to increase the production of natural DNase I, but rather it only supplements it so that the imbalance of decreased tear fluid DNase I is corrected, we expect long-term use of rhDNase1.

RhDNase is currently used as an inhaled drug in adults and children with cystic fibrosis. Patients with cystic fibrosis have experienced a change in or loss of their voice, discomfort in the throat, chest pain, red watery eyes, rash, dizziness, fever, or runny nose. Most of these are systemic side-effects that are not generally seen with eye drops. These side effects are usually mild and short-lived.

The most likely discomforts a subject may experience by having RhDNase administered as eye drops are eye burning or irritation, red watery eyes, or feeling like there is something in the eye. To see how subjects react to the study medication, their first dose will be given by the investigator in the clinic itself. Afterwards subjects will be asked to rate tolerability of the drug on the Visual Analogue Scale. Also, at each) visit, subjects will be asked to complete the Visual Analogue Scale.

An allergic reaction to the drug cannot be predicted beforehand. In event of an allergic reaction, the drug will be stopped immediately, and symptoms will be managed appropriately depending on the severity of the reaction.

Restasis, a drug used to treat DED, is held during the 14 day wash-out period and over the entire course of the study. Holding Restasis may increase the subject's risk of worsening DED.

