Participants randomized to the placebo have a risk of worsening dry eye disease. All study subjects will be encouraged to contact the research team immediately if they experience worsening of their DED.

No psychological, social, legal, or financial risk is expected from participating in the research.

There is always a risk of a loss of confidentiality.

2 Study Objectives

The objective of this study is to establish whether patients with Dry Eye Disease are able to tolerate receiving rhDNase1 0.1% eye drops four times a day for eight weeks (primary tolerability objective) and to investigate the preliminary efficacy of rhDNase1 topical eye drop solution 0.1% in treating Dry Eye Disease (primary efficacy objective).

3 Study Design

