3.2 Primary Study Endpoints

Primary Efficacy End Point: The primary end points after 8 weeks of treatment include the following: (1) the change in the Ocular Surface Disease Index (OSDI) which is a patient subjective rating scale; the Clinical Global Impression (CGI) of change in dry eye disease symptoms (physician's rating) and Subject Global Assessment (SGA) of overall change from baseline (patient's rating) will serve as anchors to OSDI, as has been described previously²⁹; (2) a mean reduction in ocular surface staining as measured by Rose Bengal dye staining and (3) the change in ocular surface redness score OR slit-lamp examination.

Primary Tolerability End Point: The change in the test substance tolerance between Day 1 (post-dose) and at weeks 2, 4, 6 and 8.

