3.2.1 Efficacy End Point: Ocular Surface Disease Index (OSDI)

The OSDI rating scale has twelve questions in three discrete areas, with responses rated on a five point scale. Subjects will complete this scale on Day 1 prior to first dose (Baseline), week 2, week 4, week 6, week 8 and week 10. The questions and scoring system are shown below:

HAVE YOU EXPERIENCED ANY OF THE FOLLOWING DURING THE LAST WEEK:

	All of the time	Most of the time	Half of the time	Some of the time	None of the time
1. Eyes that are sensitive to light?	4	3	2	1	0
2. Eyes that feel gritty?	4	3	2	1	0
3. Painful or sore eyes?	4	3	2	1	0
4. Blurred Vision?	4	3	2	1	0
5. Poor vision?	4	3	2	1	0

HAVE PROBLEMS WITH YOUR EYES LIMITED YOU IN PERFORMING ANY OF THE FOLLOWING DURING THE LAST WEEK:

	All of the time	Most of the time	Half of the time	Some of the time	None of the time	
6. Reading?	4	3	2	1	0	N/A
7. Driving at night?	4	3	2	1	0	N/A
8. Working with a computer Or bank machine (ATM)?	4	3	2	1	0	N/A
9. Watching TV?	4	3	2	1	0	N/A

HAVE YOUR EYES FELT UNCOMFORTABLE IN ANY OF THE FOLLOWING SITUATIONS DURING THE LAST WEEK:

	All of the time	Most of the time	Half of the time	Some of the time	None of the time	
10. Windy conditions?	4	3	2	1	0	N/A
11. Places or areas with Low humidity (very dry)?	4	3	2	1	0	N/A
12. Areas that are air conditioned?	4	3	2	1	0	N/A

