3.2.6 Tolerability End Point: Test Substance Tolerance (Visual Analogue Scale)

Subjects will assess their tolerance to the administration of the test medication (placebo/ study drug), utilizing a Visual Analog Scale (VAS). The VAS is a 100 mm horizontal line with verbal descriptors at either end. The VAS ratings will be completed after administration of the test medication on Day 1 (post-dose), week 2, week 4, week 6 and week 8. Subjects will place a single slash mark across the horizontal line between the end labeled “completely intolerable” (0 mm) and “easily tolerable” (100mm). The VAS rating is as follows:

Please rate the degree of comfort or lack of comfort associated with administering the eye drop by making one slash mark on the line below:

Visual Analogue Scale

On the scale of 0 to 100 seen below, please mark where you would rate your tolerability to administration of the test drug.

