6.5.2 Visit 2 Day 1 (*Randomization and First treatment visit*)

Prior to first dose (Baseline)

- Vital Signs (blood pressure taken while subject is relaxed in a sitting position for at least 3 minutes, pulse, temperature, and height and weight (at this visit only).
- Baseline Ophthalmic Examination (slit lamp examination, Ocular surface redness score)
- BSCVA (Snellen)
- OSDI
- Clinical Global Impression, Subject Global Assessment
- Record changes in concomitant medication
- Adverse events since screening visit.

Investigator/designee administers first dose

Post-Dose

- Visual Analogue Scale
- Subjects will be trained on how to self-administer the study eye drops and be given a sufficient supply to last for 2 weeks to take home.
- Subjects will receive a study diary on which to record the day/time of each dose and any adverse effects.
- Post dose evaluation for any adverse effects.

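### The primary tolerability endpoint measures change from a VAS rating made after the first randomised drop, so steady discomfort scores zero, and no between-arm comparison of VAS level is committed to

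*Combined protocol and SAP*

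**What the plan says.** Section 3.2 gives the primary tolerability endpoint as "The change in the test substance tolerance between Day 1 (post-dose) and at weeks 2, 4, 6 and 8". Section 3.2.6 sets the timing: "VAS ratings will be completed after administration of the test medication on Day 1 (post-dose), week 2, week 4, week 6 and week 8". The 100 mm line runs from the intolerable end (0) to the easily tolerable end (100), and the item reads "Please rate the degree of comfort or lack of comfort associated with administering the eye drop". Section 1.5 confirms the order on Day 1. The first dose is given in clinic, and then "Afterwards subjects will be asked to rate tolerability of the drug on the Visual Analogue Scale". Section 6.5.2 lists the VAS after that dose, and no earlier VAS is scheduled.

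Elsewhere the protocol reserves the word baseline for values taken before dosing. Section 3.2.1 says of the OSDI "Subjects will complete this scale on Day 1 prior to first dose (Baseline", and Section 6.5.2 heads its pre-dose list "Prior to first dose (Baseline".

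Section 7.2 applies descriptive statistics, where appropriate, to all primary and secondary endpoints. It names the OSDI for its paired signed-rank test. It promises 95% confidence intervals between drug and placebo for primary efficacy, primary safety and the secondary endpoints; primary tolerability is not in that list. The objective in Section 2 is "to establish whether patients with Dry Eye Disease are able to tolerate receiving rhDNase1 0.1% eye drops four times a day for eight weeks".

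**The concern.** The reference value is measured under treatment, so any effect of drug on comfort at the first drop is inside it and is subtracted from every later rating. What remains is adaptation or deterioration. The amount of discomfort is lost.

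This is the pattern the protocol itself expects. Section 1.5 lists burning, irritation and foreign-body feeling among the likeliest discomforts, and has the first dose given in clinic to see how subjects react. The VAS is also the only scale in the plan that rates comfort on instillation along a continuum. If the endpoint is reported as written, a drop that stings from the first dose to the last gives the same result as one that never stings. The trial could then report no change in tolerance without saying how comfortable the drug was compared with its vehicle.

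**Working it through.** **Inputs from the documents.** VAS range 0 to 100 mm, higher meaning better tolerated (3.2.6). Ratings on Day 1 post-dose and at weeks 2, 4, 6 and 8 (3.2, 3.2.6). Intended completers: at least 30 per arm (7.1). Two-sided 0.05 (7.2). The documents give no VAS mean, SD, margin or power, so there is no planned figure to reproduce. SDs, deficits and correlations below are assumptions.

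**Step 1: one subject.** Change = later rating minus Day 1 rating. A subject at 0 mm on all five occasions has 0 - 0 = 0. A subject at 100 mm on all five has 100 - 100 = 0. No assumption is needed.

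**Step 2: between arms.** Let D1 and Dk be the drug-minus-vehicle difference in mean VAS on Day 1 and at visit k. The contrast of change is Dk - D1.

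| Pattern (assumed) | D1 | D at week 8 | Change contrast |
|---|---|---|---|
| Constant 10 mm deficit | -10 | -10 | 0 |
| Constant 20 mm deficit | -20 | -20 | 0 |
| Constant 30 mm deficit | -30 | -30 | 0 |
| Shrinks but persists | -20 | -10 | +10 |
| Gone by week 8 | -20 | 0 | +20 |
| Emerges under treatment | 0 | -20 | -20 |

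Change captures the last row fully. It misses the constant rows, and it would favour drug in the two rows where an early deficit shrinks. Week 8 level alone would miss the row where the deficit has gone, so levels are needed at every visit, including Day 1.

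**Step 3: precision of a level comparison.** Half-width of the 95% CI = t(0.975, 58) x SD x sqrt(2/30), with t = 2.002. At SD 20: 2.002 x 5.164 = 10.3 mm. At SD 30: 2.002 x 7.746 = 15.5 mm.

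**Step 4: chance that a single-visit level comparison shows drug worse** (noncentral t, 30 per arm, two-sided 0.05):

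| True deficit | SD 20 | SD 25 | SD 30 |
|---|---|---|---|
| 20 mm | 97% | 86% | 72% |
| 10 mm | 48% | 33% | 25% |

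A between-arm test of change would show a constant deficit in only 2.5% of trials at any SD, which is its one-sided error rate. If 20% of the 72 are lost, 57.6 remain. With 29 per arm the 20 mm row becomes 96%, 85% and 70%.

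**Step 5: adjusting for the Day 1 VAS.** Using the Day 1 post-dose rating as a covariate does not rescue the comparison. With a constant deficit D and within-arm correlation r between visits, the expected adjusted difference is D x (1 - r). For total and within-subject SDs of 25 and 10, 20 and 10, and 25 and 15, r = 1 - (within SD / total SD)² = 0.84, 0.75 and 0.64. A true 20 mm deficit is then estimated at 20 x 0.16 = 3.2, 20 x 0.25 = 5.0 and 20 x 0.36 = 7.2 mm.

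**The case against.** The strongest reply is that tolerability is covered elsewhere. Completion of eight weeks of therapy (3.4) closely matches the objective in Section 2 and has a between-arm confidence interval under 7.2. The Study Summary names completion, not the VAS, as the primary safety measure. Adverse symptoms go into diaries that staff review at visits (5.5, 8.10), subjects are reminded to report them (8.1), Day 1 includes "Post dose evaluation for any adverse effects", and every event is graded mild, moderate or severe (8.2). Persistent burning in a subject who continues can therefore be recorded with an intensity. This stands, and it limits the reach of the point. What it leaves open is that completion counts an uncomfortable completer as a success, that subjects are not prompted about adverse events (8.1), and that three grades are coarser than a 100 mm scale.

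Second, the descriptive statistics promised in 7.2 may well show mean VAS by arm and visit. They may, but the endpoint they describe is change, and nothing commits to levels by arm.

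Third, comfort of a drop cannot be rated before a drop is given, so Day 1 post-dose is the earliest reference available, and change from it is a legitimate question about adaptation or emerging intolerance. That is correct, and is a reason to keep change as a secondary description. Section 3.2 also never calls this rating a baseline.

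A reader might infer that the plan will make a less comfortable drug look better than vehicle. The documents do not support that. The +10 and +20 mm results in the table arise only if change is compared between arms, and 7.2 states no such comparison for the VAS.

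**Conclusion.** The point holds as a weakness in how the endpoint is defined and analysed. Zero change under steady discomfort follows from the wording of 3.2 alone and depends on no assumed value. The absence of a committed between-arm comparison of VAS level follows from 7.2. The power and precision figures are illustrations that rest on assumed SDs of 20 to 30 mm. They also show that a level comparison with 30 per arm has limited sensitivity to a 10 mm deficit, although its estimate is not fixed at zero.

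It would go too far to conclude that the trial cannot assess tolerability or that discomfort is concealed. Completion and adverse events address whether patients can continue, and the VAS levels are collected in both arms. The revision should be made because it is cheap and because, as written, the stated endpoint cannot show the discomfort the protocol most expects.

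**What to change.** In 3.2 and 7.2, define the tolerability endpoint as the between-arm difference in VAS level, drug minus vehicle with a 95% confidence interval, at Day 1 post-dose and at weeks 2, 4, 6 and 8. Give the number rated per arm at each visit, because later levels come only from those still attending. Add a line to 7.3 so that the Day 1 rating is reported in all dosed subjects, including those the two-week treatment rule would exclude. State that the Day 1 post-dose VAS is not a baseline value and is not to be used for the baseline adjustment in 7.2. Keep change from Day 1 as a secondary description of adaptation or emerging intolerance.

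The cost is some rewording and five level estimates in place of four change measures. Each is imprecise, as shown above, and should be read as an estimate. Every rating is already scheduled, so no new data are required.

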Net	Neutrophil extracellular trap
OSDI	Ocular Surface Disease Index
Otc	Over the counter
QID	Four times per day
rhDNase1	Recombinant human deoxyribonuclease I
SAE	Serious Adverse Event
SGL	Subject Global Assessment
SP	Substance P
UIC	University of Illinois at Chicago
VA	Visual Acuity
VAS	Visual Analog Scale

Study Summary

Title	A Phase I/II Randomized Placebo-Controlled, Double-Blind Single-Center, tolerability and preliminary efficacy clinical trial of recombinant human deoxyribonuclease (rhDNase) eye drops in patients with dry eye disease.
Short Title	DNase treatment for dry eyes
Protocol Number	UIC-CNBL-1001
Phase	Phase I/II
Methodology	Double-blind
Study Duration	10 weeks
Study Center(s)	Single-center
Objectives	To evaluate the tolerability and preliminary efficacy of rhDNase1 eye drops in patients with Dry Eye Disease.
Number of Subjects	72 (study drug at least 30, placebo at least 30)
Diagnosis and Main Inclusion Criteria	Men and women ≥ 18 years of age with a diagnosis of established Dry Eye Disease, with Schirmer I < 10 , Ocular surface staining ≥ 1 and OSDI mild (≥ 13).
Study Product, Dose, Route, Regimen	Study drug: rhDNase1 (Pulmozyme®), 0.1% eye drops four times a day for eight weeks. Control: drug vehicle eye drops four times a day for eight weeks.
Duration of administration	8 weeks
Reference therapy	None
Statistical Methodology	Descriptive statistics will be used for all primary and safety endpoints, when appropriate. A Wilcoxon test will be used to compare changes in subjective symptoms from Baseline to follow-up values at 2 weeks, 4 weeks, 6 weeks, 8 weeks and 10 weeks. Primary efficacy measure is the change in the OSDI reported between Baseline and Week 8. Primary safety measure is the proportion of patients at week 8 who were able to successfully complete a full eight weeks of therapy with topical administration four times per day (q.i.d).

1 Introduction

This document is a protocol for a human research study. This study is to be conducted according to US and international standards of Good Clinical Practice (FDA Title 21 part 312 and International Conference on Harmonization guidelines), applicable government regulations and Institutional research policies and procedures.

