3.4 Primary Safety Endpoints

Safety assessments include Vital Signs, recording of all complications and adverse events, as well as ophthalmic exam findings. All ocular and non-ocular adverse events will be assessed for severity and relationship to the investigational product.

Primary safety endpoint:

- The proportion of subjects at week 8 who were able to successfully complete a full eight weeks of therapy with topical administration four times per day (q.i.d.)

Secondary safety endpoint:

- All adverse events reported, whether deemed related to treatment, or not.
- Clinically significant changes in vital signs or ophthalmic examination from baseline.

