7.2 Statistical Methods

Descriptive statistics will be used for all primary and secondary endpoints, when appropriate.

We will define outcome measures on the basis of the change for each subject from baseline to each follow-up point, controlling for chance imbalances in the mean baseline values between treatment groups. A Wilcoxon Signed-rank test will be used for paired comparison of quantitative variables (OSDI score) between the baseline and each post-baseline time points. Chi-square test will be used to compare qualitative variables (Investigator's rating scale/ changes in concomitant medications) between the 2 groups. Two-sided $P < .05$ will be considered statistically significant for all comparisons. 95% Confidence interval will be provided for comparison between the investigational drug and placebo for the primary efficacy, the primary safety, and the secondary endpoints.

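### The primary tolerability end point is a VAS change at four visits with no deciding visit, no named test and no planned between-arm interval, and its relation to eight-week completion is not stated

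*Combined protocol and SAP*

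**What the plan says.** Section 2 sets the tolerability question: whether patients "are able to tolerate receiving rhDNase1 0.1% eye drops four times a day for eight weeks (primary tolerability objective").

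Section 3.2 gives the primary tolerability end point as "The change in the test substance tolerance between Day 1 (post-dose) and at weeks 2, 4, 6 and 8". Section 3.2.6 sets the timing: "The VAS ratings will be completed after administration of the test medication on Day 1 (post-dose), week 2, week 4, week 6 and week 8". The scale runs from 0 mm (worst) to 100 mm (best), and no cut-off is given for a tolerated drop. The efficacy end points in Section 3.2 are tied to the end of eight weeks of treatment; the VAS is not tied to any single visit.

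Section 3.4 lists as the primary safety endpoint "The proportion of subjects at week 8 who were able to successfully complete a full eight weeks of therapy", on the four-times-daily regimen. The Study Summary repeats it ("Primary safety measure is the proportion of patients at week 8 who were able to successfully complete a full eight weeks of therapy") and does not mention the VAS in its statistical methodology.

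Section 7.2 begins "Descriptive statistics will be used for all primary and secondary endpoints, when appropriate". It then says "A Wilcoxon Signed-rank test will be used for paired comparison of quantitative variables (OSDI score"), without naming the VAS, and adds that two-sided P < .05 "will be considered statistically significant for all comparisons". It promises a 95% confidence interval for drug against placebo for primary efficacy, primary safety and the secondary endpoints. Primary tolerability is not on that list.

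**The concern.** Tolerability is the first-named objective. The end point carrying that label has four time points and no rule for choosing or combining them. It also has no named test, and the plan does not say whether the comparison is within or between arms. The measure closest to the wording of the objective sits under a different label, and nothing says how the two are to be read together.

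The emphasis can therefore be settled after the data are seen. One nominally significant visit could be put forward as a tolerability finding, or a quiet Week 8 result or a good completion rate could be put forward instead. The reader of the report could not tell which of these had been intended.

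**Working it through.** The plan states no power, error rate, VAS standard deviation or tolerability margin, so it has no figure of its own to reproduce. Three checks follow.

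**1. Chance of a stray signal across four visits**

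Inputs: four visits (Section 3.2) and two-sided 0.05 per comparison with no adjustment (Section 7.2). Two things are assumed: that each visit is tested between arms, and the correlation among the four change contrasts. If all visits are equally correlated, sharing one Day 1 value implies a correlation of 0.5 between changes, so 0.5 is a natural middle case.

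- Independent contrasts, either direction: 1 − 0.95⁴ = 0.185.
- Independent contrasts, drug worse only: 1 − 0.975⁴ = 0.096.
- Correlated contrasts: 1 minus the probability that four equally correlated standard normal statistics all stay inside ±1.96 (or, for drug worse, all stay on the near side of one limit), by numerical integration.

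| Assumed correlation | Any P < .05, either direction | Any P < .05, drug worse |
|---|---|---|
| 0 | 18.5% | 9.6% |
| 0.5 | 15.6% | 7.8% |
| 0.7 | 13.0% | 6.5% |
| 0.8 | 11.4% | 5.7% |

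One contrast named in advance gives 5% and 2.5%.

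**2. What the change score measures**

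The reference value is taken after the first dose, so it is already on treatment. Suppose (all assumed) that drug scores 18 mm below vehicle after the first dose, and that the deficit fades to 15, 12, 8 and 4 mm at Weeks 2, 4, 6 and 8. The contrasts in change from Day 1 are then:

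- 18 − 15 = +3 mm
- 18 − 12 = +6 mm
- 18 − 8 = +10 mm
- 18 − 4 = +14 mm

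All four favour drug, although drug is less comfortable at every visit. Take 30 per arm (the completer target in Section 7.1), an assumed VAS SD of 20 mm and a between-visit correlation of 0.5. The SD of change is 20 × √(2 × (1 − 0.5)) = 20 mm and the standard error is 20 × √(2/30) = 5.16 mm. The chance of P < .05 is then about 9%, 21%, 48% and 76% at Weeks 2 to 8. With no deficit after the first dose, the same later deficits would give contrasts of −15, −12, −8 and −4 mm, reversing both the direction and the order of the visits. The change score cannot be interpreted without the Day 1 values by arm.

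**3. Completion and the analysis population**

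Section 7.3 keeps only subjects with at least two weeks of treatment and a Week 2 visit. Take 36 per arm (half of 72) with 7 stopping (20% of 36 is 7.2), and assume 3 of the 7 stop before Week 2. Completion is 29/36 = 80.6% among all dosed subjects but 29/33 = 87.9% in the Section 7.3 population. Early intolerance is what drops out.

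**The case against.** The strongest reply is that the labels do pair up. Section 2 has a tolerability objective, Section 3.2 a tolerability end point, and Section 3.2.6 heads the VAS as the tolerability measure, while completion is called safety in both places where it appears. A reader might infer five rival primary tolerability contrasts. The documents do not support that count: there are four labelled tolerability contrasts, plus one primary safety measure whose wording happens to fit the objective better.

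The second reply is that Section 7.2 puts description first, names only the OSDI for the signed-rank test, and promises no between-arm VAS comparison. That stands. The rates in the working apply to tests that the plan permits under its general significance rule but does not specify. A reader might infer an inflated confirmatory error rate, but there is no confirmatory tolerability test to inflate. Nor does the plan say that a non-significant Week 8 VAS would count as tolerated.

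Third, discomfort that fades over the visits is a real time course. Different results at different visits are then not a contradiction, and reporting every visit is right.

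Finally, a reader might conclude that completion alone should decide. That is doubtful. Sections 5.6 and 5.7 remove subjects who restart anti-inflammatory therapy after clinical worsening, and Section 1.5 warns of worsening on placebo. Completion therefore mixes comfort with disease control and could favour drug for reasons unrelated to tolerability.

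What remains is that no deciding visit, no between-arm VAS estimate and no link between the two measures is written down.

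**Conclusion.** The point holds as a gap in specification. The labelled primary tolerability end point has four visits and no deciding one, no named test and no promised drug-versus-placebo interval. The measure nearest the objective is filed under safety with no stated relation to it.

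If the visits are tested between arms, the chance of at least one nominally significant result with no true difference is about 11% to 19% in either direction, and about 6% to 10% for drug worse. These ranges rest on an assumed equal correlation from 0.8 down to 0. They measure room for interpretation in a largely descriptive Phase I/II trial. The Day 1 example rests wholly on assumed values and shows only that the direction of the change contrast depends on the first-dose response.

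Naming one contrast will not by itself decide whether the drops are tolerated, because the documents give no criterion for that.

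**What to change.** In the Study Summary and Sections 3.2 and 7.2:

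- Name one VAS contrast in advance, for example change to Week 8, drug versus vehicle, with its 95% confidence interval, and name the method.
- Report Weeks 2, 4 and 6 as between-arm estimates with intervals and no significance claim.
- Report the Day 1 post-dose VAS by arm, because that reference is already on treatment.
- Report completion, drug minus vehicle with its 95% confidence interval, among all randomised and dosed subjects rather than the Section 7.3 population. Tabulate the reasons for stopping, separating intolerance from disease worsening.
- State how the VAS contrast and completion together answer the Section 2 objective.

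Section 4.4.2 asks subjects who withdraw before Week 8 to complete the tolerance scale. The plan should also say whether that value counts as the Week 8 value.

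The cost is wording only, with no new visits, data or subjects. The one small loss is that a VAS difference at an early visit can no longer stand alone as a significant finding, though it is still reported.
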